 - ✓ Diseases of bones or joints of the lower limbs, that can affect the course of the ulcer according to the researcher
 - ✓ Malignant neoplasm
- Treatment with drugs that can cause edema of the lower extremities (calcium channel blockers, hormonal agents, NSAIDs, etc.)
- History of deep vein thrombosis (within 1 year prior to inclusion)
- History of superficial venous thrombophlebitis (within 3 months prior to inclusion)
- The patient underwent surgery for CVD in the previous 3 months
- Patient cannot walk (regardless of the cause)
- Poor predicted adherence to treatment
- Participation in an intervention study in the previous 3 months
- For women: pregnancy or breastfeeding, or willing to become pregnant within at least 2 months after the end of the study
- The necessity, according to the doctor-investigator, of treatment with any diosmin-containing drug outside of its approved indications (off-label) or in the presence of contraindications stated in the instruction for medical use of this drug relevant in the Russian Federation at the time of the study, within the scope of this protocol
- Use of a topical agent that is contraindicated in case of compromised skin integrity

Exclusion criteria:

- Withdrawal of the informed consent
- Pregnancy or willingness to become pregnant within at least 2 months after the end of the study
- Indications for surgery (including sclerotherapy)
- Serious violation or non adherence to the prescribed therapy/ regimen
- Use of prohibited drugs that can cause edema of lower extremities (calcium channel blockers, hormonal agents, NSAIDs, etc.)

Treatment effectiveness criteria

1. Venous Clinical Severity Score (VCSS)
2. Clinical class of CVD by CEAP classification (2020)
3. Changes in the parameters of skin condition:
 - area of the reference venous ulcer (measured by LesionMeter)
 - changes in *status localis*
 - changes in symptoms (pain) as assessed by visual analogue scale (VAS).
4. The quality of life (QoL) questionnaire CIVIQ-14 (**Appendix 2**).

Data collection during the study

At scheduled visits participating physicians will be assessing and collecting parameters of interest which they should input in eCRF.

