At the inclusion visit (V0) following data will be collected: a signed consent form, demographic characteristics (age, sex, body weight, BMI and height), eligibility of a patient to the inclusion/ non inclusion criteria, history and risk factors of CVD, history and current status of taking drugs and non drug treatments for CVD; all parameters of VCCS including characteristics of symptoms for CVD such as pain, hyperaemia, characteristics of the ulcer(s) etc., characteristics of the reference ulcer; results of evaluation of the stage of the disease (CEAP classification); results of DUS characterizing venous reflux and its location, presence or absence of venous occlusion and its location; skin condition/ pain severity will be patient-reported evaluation with VAS, results of a self-assessed quality of life status performed by completing CIVIQ 14 questionnaire; assigned treatment for CVD including data on administered topicals, systematic pharmacotherapy, compression therapy.

At visits 1; 2; 3 (V1; V2;V3) following data will be collected: eligibility of a patient to exclusion criteria; characteristics of the ulcer(s) etc., characteristics of the reference ulcer; skin condition/ pain severity will be patient-reported evaluation with VAS; any changes in the administered treatment for CVD including usage of topicals, usage of systematic pharmacotherapy, usage of compression therapy; information regarding any adverse event/ adverse drug reaction or special situations (see chapter Safety Considerations).

At visit 4 (V4) following data will be collected: eligibility of a patient to exclusion criteria; all parameters of VCCS including characteristics of symptoms for CVD such as pain, hyperaemia, characteristics of the ulcer (s) etc., characteristics of the reference ulcer; results of evaluation of the stage of the disease (CEAP classification); skin condition/ pain severity will be patient-reported evaluation with VAS; results of a self-assessed quality of life status performed by

completing CIVIQ 14 questionnaire; any changes in the administered treatment for CVD including usage of topicals, usage of systematic pharmacotherapy, usage of compression therapy; information regarding any adverse event/ adverse drug reactions or special situations (see chapter Safety Considerations).

SCHEDULE OF THE STUDY

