Actions	V0 visit (inclusion)	V1 visit (1 month after V0 visit)	V2 visit (3 months after V0 visit)**	V3 visit (interim), if applicable*	V4 visit (6 months after V0 visit)
Informed consent	+				
Inclusion/ Non inclusion criteria	+				
Exclusion criteria		+	+	+	+
Reporting of AEs		+	+	+	+
Completion of the CRF	+	+	+	+	+
VCSS	+				+
CEAP clinical class	+				+
Skin changes (by VAS)	+	+	+	+	+
Status localis	+	+	+	+	+
DUS (presence of reflux)	+				
QoL assessment (CIVIQ-14)	+				+
Data on the treatment and its change	+	+	+	+	+
Venoactive drug	+	+	+	+	+
Compression hosiery	+	+	+	+	+
Topical treatment	+	+	+	+	+

* The visit takes place if the venous ulcer is healed between V2 and V4 visits

**The visit can be replaced by telephone interview which remains at discretion of the doctor-investigator

Safety considerations.

1. Definitions

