2.3. Responsibilities of the Sponsor/Marketing Authorization Holder

Independently of the regulatory obligations of the treating physician, the sponsor/MAH must report the pharmacovigilance data to the appropriate authorities in accordance with the Good Vigilance Practice and local regulations.

Cases are closed when an adverse event has recovered or patient's condition was stabilised and the report is deemed sufficiently detailed for adequate medical analysis of the case.

Statistical parameters

Statistical analysis:

The baseline characteristics will be analyzed in all included patients regardless of the patient's adherence to the protocol procedures (intention-to-treat analysis). The analysis of the study results will be carried out using the SPSS 12.0 software package (SPSS Inc., USA). Data entry errors will be corrected before the start of statistical processing. Quantitative parameters will be presented taking into account the distribution of raw data, in the form of arithmetic mean \pm standard deviation for parametric, and in the form of a median (25; 75 percentile) for nonparametric variables. Accordingly, a comparison on quantitative parameters between the

groups with different adherence will be carried out using the Student's t-test for independent samples or using the Mann-Whitney U-test.

For multiple comparisons, a correction for continuity will be implemented. The changes in quantitative parameters during the follow-up period will be evaluated using the Student's t-test for paired samples or its nonparametric analogue, Wilcoxon test.

Changes in the quantitative parameters, both in the independent groups and during the follow-up period, will be evaluated as the difference between the mean values and the corresponding 95% confidence intervals.

Differences between the groups by the mean score of the VAS, VCSS, and CIVIC-14, and by an integrated index of skin changes (lesion area, ultrasound data) will be carried out using two-way analysis of variance with repeated measures, in order to compare scores before and after the treatment.

Safety will be assessed in all patients who received at least one dose of any venoactive drug during the study (studied drugs).

Adverse events will be recorded and analyzed in patients, and all adverse events, serious adverse events, adverse reactions, serious adverse reactions and special situations will be listed.

Ethical considerations:

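### Patients can be excluded after enrolment for reasons that may relate to outcome or adherence, with no effectiveness population defined and no rule on further observation

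*Combined protocol and SAP*

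**What the plan says.** The Exclusion criteria are a separate list from the non-inclusion criteria. Three of their entries matter here: "Indications for surgery (including sclerotherapy", "Serious violation or non adherence to the prescribed therapy/ regimen" and "Use of prohibited drugs that can cause edema of lower extremities". Entry already requires that no CVD procedure is planned, so the surgical criterion acts on indications that arise or are recognised after enrolment.

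The Schedule of the study applies the exclusion check at V1 (month 1), V2 (month 3), V3 and V4 (month 6). V2 need not be in person: "The visit can be replaced by telephone interview which remains at discretion of the doctor-investigator". V3 is conditional: "The visit takes place if the venous ulcer is healed between V2 and V4 visits". VCSS and CEAP class are taken only at V0 and V4. At V4 the exclusion check is listed together with the outcome assessments: "At visit 4 (V4) following data will be collected: eligibility of a patient to exclusion criteria; all parameters of VCCS". No early-termination assessment is scheduled.

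The Statistical analysis section names two populations. For baseline: "The baseline characteristics will be analyzed in all included patients", whatever their adherence, with the label intention-to-treat. For safety: "Safety will be assessed in all patients who received at least one dose of any venoactive drug during the study". It names none for effectiveness, and gives no rule for missing data, withdrawal or non-response.

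Two of the three primary variables are percentages of patients (6-month healing of the reference ulcer, and reduction in CEAP class), with no further definition of the denominator. Secondary goal 3 reports the percentage still taking the prescribed venoactive drug at V1, V3 and V4. The Statistical analysis section plans comparisons between groups that differ in adherence.

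**The concern.** Applied as written, the three criteria take patients out of the program for reasons that may be connected with the result. An ulcer that stays open is a plausible reason for a physician to record a surgical indication, although the documents do not say so. Poor adherence is itself something the program sets out to describe.

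There is no comparison arm in which similar losses could offset these, so the percentage is the result. If the denominator is not set in advance, it can be chosen after the data are seen. If only remaining patients are counted and removal depends on outcome, the reported healing and CEAP-reduction percentages do not describe the enrolled cohort. VCSS change would likewise describe only those with a V4 value.

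Removing the seriously non-adherent raises a further problem. It takes away the patients most informative for the percentage continuing therapy and for the comparison of adherence groups.

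**Working it through.** **The plan's own figure.** 90 physicians × at least 5 patients each gives the planned 450. This is recruitment arithmetic. The plan states no precision target, power or allowance for exclusions, so there is nothing further to reproduce.

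**What an exclusion costs, by visit, if observation then stops.**
- At V1, V2 or an unscheduled contact: no later VCSS or CEAP class and no 6-month ulcer status. If V2 is a telephone call, the ulcer is not examined that day.
- At V3: closure has been found, because V3 happens only after healing, but there is no later VCSS or CEAP class.
- At V4: the schedule collects everything at the same visit. Nothing says these values are dropped, and nothing says they are kept.

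**Inputs for the illustration.** True healing p = 0.45 and p = 0.83, the two ends of the 24-week range in the Rationale; N = 450. The removal shares are assumptions, because the documents give none: rn among patients who would not heal, rh among those who would.

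**Formulas.**
- Healing among those remaining: p(1−rh) / [p(1−rh) + (1−p)(1−rn)].
- Healing if every removed patient is counted as not healed: p(1−rh).
- 95% half-width: 1.96 × √[p(1−p)/450], which is 4.6 points at 45% and 3.5 at 83%.

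**Example, rn = 0.25 and rh = 0.10.**
- p = 0.45: 0.405 / (0.405 + 0.4125) = 49.5%. Removed: 450 × (0.045 + 0.1375) = 82.1.
- p = 0.83: 0.747 / (0.747 + 0.1275) = 85.4%. Removed: 450 × (0.083 + 0.0425) = 56.5.

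Results in percent, with the difference from true healing in points in brackets:

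| rn / rh | p = 45%, remaining only | p = 45%, removed = not healed | p = 83%, remaining only | p = 83%, removed = not healed |
|---|---|---|---|---|
| 10% / 4% | 46.6 (+1.6) | 43.2 (−1.8) | 83.9 (+0.9) | 79.7 (−3.3) |
| 25% / 10% | 49.5 (+4.5) | 40.5 (−4.5) | 85.4 (+2.4) | 74.7 (−8.3) |
| 10% / 10% | 45.0 (0) | 40.5 (−4.5) | 83.0 (0) | 74.7 (−8.3) |
| 10% / 25% | 40.5 (−4.5) | 33.75 (−11.25) | 80.3 (−2.7) | 62.25 (−20.75) |

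The remaining-only columns show bias from selective removal. It can be positive, zero or negative, and in the more selective cases it comes close to the half-width. The removed-as-not-healed columns are no closer to the true rate in any row. That rule alone does not repair lost observation; continued observation does.

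**Upper bound.** Suppose 10% (45 of 450) are excluded and all are unhealed. Dropping them turns 202/450 = 44.9% into 202/405 = 49.9%, and 374/450 = 83.1% into 374/405 = 92.3%. In the second case this removes 45 of only 76 unhealed patients (59%), so it is an extreme.

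The bias in VCSS change cannot be computed from the documents.

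**The case against.** The best case for the plan is that it describes one cohort, with no hypothesis or threshold on the healing percentage. Stopping at a surgical indication is then a defensible way to describe drug and compression therapy without procedures. Known candidates for surgery are screened out at entry, and duplex ultrasound is not repeated without a specific reason, so later indications may be few. Ulcer characteristics and exclusion status are both recorded at V1 to V4, so much of a table of exclusions by ulcer status needs no new data. The planned comparison by adherence shows that less adherent patients are at least partly meant to be analysed.

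Much of this stands, and it limits the size of the point. It does not supply an effectiveness population or a rule on observation after exclusion. The adherence comparison also sits badly with an exclusion for serious non-adherence.

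The intention-to-treat label does not close the gap. The subject of that sentence is baseline characteristics, and even read broadly it does not say how a patient excluded for surgery is scored.

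A reader might infer three stronger things that the documents do not support:
- **That the plan overstates healing.** The link between an open ulcer and a surgical indication is inference. An unhealed patient has no scheduled check between month 3 and V4, while one who heals in that window has V3 with its exclusion check, so removal could also fall on healers.
- **That V4 values are lost for patients flagged at V4.** No section says so.
- **That the gap between the two counting rules (9.0 and 10.7 points in the 25%/10% case) is bias.** It is the distance between two definitions of the result.

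**Conclusion.** The point holds as a gap in specification with a plausible but unquantified bias. The plan states three outcome- or adherence-related grounds for exclusion. It leaves open whether observation continues and who counts in the effectiveness percentages. Under the assumed removal rates, bias in the healing percentage runs from −4.5 to +4.5 points at 45% true healing and from −2.7 to +2.4 at 83%. It is zero when removal is unrelated to healing and small when removal is light. The actual size and direction cannot be known from the documents. No error rate or power is affected; what suffers is how far the reported percentages, and the adherence results, can be read as describing the enrolled patients. The change is worth making because it is cheap, not because a large distortion has been shown. Confidence is moderate.

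**What to change.** 1. Treat a surgical indication, serious non-adherence and prohibited drug use as events recorded with date and reason, not as reasons to stop observation. Continue the routine visits to V4, with ulcer status, VCSS and CEAP class, unless consent is withdrawn.
2. In the Statistical analysis section, make all included patients the main denominator for 6-month healing and CEAP reduction, using observed status wherever it exists. For healing, count a procedure before closure, or no documented closure, as not healed, and say that this is the chosen composite definition. For CEAP reduction, state how patients with a procedure or no V4 class are counted; following the healing rule is a choice of estimand, not a correction.
3. Report VCSS change with the number of patients who have a V4 value.
4. Report how many patients met each criterion, by ulcer status at that time, and add a sensitivity analysis excluding them.

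The cost is a reworded criteria block, one dated eCRF item, a short denominator paragraph, and visits that are already scheduled. Treatment does not change. The downsides are a possibly lower reported healing rate and some post-procedure V4 values in the main description, which the sensitivity analysis separates out.

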1.1 Pharmacovigilance information

Pharmacovigilance data include any unintended or adverse event associated with the use of a medicinal product in humans, whether or not considered drug related, including the following **special situations** (situations where no adverse event occurred but information needs to be collected):

- exposure during pregnancy or breastfeeding;
- overdose, abuse, misuse, off-label uses, medication error, occupational exposure (including professional one);
- suspected transmission of an infectious agent via a medicinal product;
- unexpected beneficial action of the drug;
- lack of the treatment efficiency of drug.

1.2. Adverse Event (AE)

Adverse event is any untoward medical occurrence in a patient or a clinical-trial subject who received the medicinal product, which does not necessarily have a causal relationship with the use of this medicinal product.

An adverse event can therefore be any unfavourable and unintended sign (e.g. an abnormal laboratory finding), symptom, or disease temporally associated with the use of a medicinal product, whether or not considered related to the medicinal product.

1.3. Adverse (drug) reaction (ADR)

Adverse reaction (synonyms: Adverse drug reaction, suspected adverse (drug) reaction, Adverse effect, Undesirable effect) is a response to a medicinal product which is noxious and unintended.

“Response” in this context means that a causal relationship between a medicinal product and an adverse event is at least a reasonable possibility.

Adverse reactions may arise from use of the product within or outside the terms of the marketing authorization or from occupational exposure. Conditions of use outside the marketing authorization include off-label use, overdose, misuse, abuse and medication errors.

1.4. Serious adverse (drug) reaction (SADR)

Serious adverse reaction is an adverse reaction, which results in death, is life-threatening, requires in-patient hospitalisation or prolongation of existing hospitalisation, results in persistent or significant disability or incapacity, or is a congenital anomaly/birth defect.

“Life threatening” in this context refers to a reaction in which the patient was at risk of death at the time of the reaction; it does not refer to a reaction that hypothetically might have caused death if more severe.

Medical and scientific judgement should be exercised in deciding whether other situations should be considered serious reactions, such as important medical events that might not be immediately life threatening or result in death or hospitalisation but might jeopardise the patient or might require intervention to prevent one of the other outcomes listed above.

Examples of such events are intensive treatment in an emergency room or at home for allergic bronchospasm, blood dyscrasias or convulsions that do not result in hospitalisation or development of dependency or abuse.

Any suspected transmission via a medicinal product of an infectious agent is also considered a serious adverse reaction.

2. Responsibilities

2.1. Events to be reported

All available information about the following reported events occurring during the study will be recorded:

- All serious adverse drug reactions related to any Servier drug and/or to other venoactive drugs
- All non-serious adverse drug reactions related to any Servier drug and/or to other venoactive drugs
- All reports about special situations (see 1.1)
- All adverse events

2.2. Responsibilities of the treating physician

In prospective studies, at medical visits, the treating physician will ask the patient participating in the study to indicate whether or not an adverse event (serious or not) has occurred.

The treating physician has to assess the causal relationship between an adverse event and a drug intake, as well as the seriousness criteria and later on the outcome of the event.

In case of Adverse Events, Adverse Drug Reactions or special situations that occurs during the study (both serious and non-serious), the treating physician must complete the "**Adverse event / Adverse drug reaction / Special Situation Reporting Form**" (**Appendix 1**) without waiting for the clinical outcome or the results of additional investigations.

When assessing the quality of life using the EQ-5D, the treating physician should evaluate data (patient's answers), their clinical relevance, and fill out the " Adverse event / Adverse drug reaction / Special Situation Reporting Form" if he/she considers these data as AE, ADR or a special situation.

If the event is serious, it will be notified immediately (same or next working day at the latest) to Servier company in Russia via e-mail to address [contact] or by fax to number [name]. The anonymized copies of all the available and relevant laboratory findings, hospitalisation reports or other investigation results performed in connection with the adverse event should be attached to the form.

All other events should be reported by a treating physician within 2 working days.

In case there is an ADR related to a non-Servier venoactive drug, the treating physician must report the pharmacovigilance data to the appropriate authorities in accordance with the Good Vigilance Practice and local regulations

The same rules apply for the transferring of additional information about the event.

The treating physician must ensure the appropriate follow-up of the patient depending on the nature of event, until it resolves. The treating physician will continue to notify follow up data according to timeframes defined above.

If a treating physician does not follow-up a patient anymore (i.e. in case of hospitalisation followed by the treatment by specialist or the participant's general practitioner,...), he/she will do every effort to contact the specialist or department in charge of follow-up of the patient, so as to have additional information and report it to Servier company in Russia.

2.3. Responsibilities of the Sponsor/Marketing Authorization Holder

Independently of the regulatory obligations of the treating physician, the sponsor/MAH must report the pharmacovigilance data to the appropriate authorities in accordance with the Good Vigilance Practice and local regulations.

Cases are closed when an adverse event has recovered or patient's condition was stabilised and the report is deemed sufficiently detailed for adequate medical analysis of the case.

Statistical parameters

Statistical analysis:

The baseline characteristics will be analyzed in all included patients regardless of the patient's adherence to the protocol procedures (intention-to-treat analysis). The analysis of the study results will be carried out using the SPSS 12.0 software package (SPSS Inc., USA). Data entry errors will be corrected before the start of statistical processing. Quantitative parameters will be presented taking into account the distribution of raw data, in the form of arithmetic mean \pm standard deviation for parametric, and in the form of a median (25; 75 percentile) for nonparametric variables. Accordingly, a comparison on quantitative parameters between the

groups with different adherence will be carried out using the Student's t-test for independent samples or using the Mann-Whitney U-test.

For multiple comparisons, a correction for continuity will be implemented. The changes in quantitative parameters during the follow-up period will be evaluated using the Student's t-test for paired samples or its nonparametric analogue, Wilcoxon test.

Changes in the quantitative parameters, both in the independent groups and during the follow-up period, will be evaluated as the difference between the mean values and the corresponding 95% confidence intervals.

Differences between the groups by the mean score of the VAS, VCSS, and CIVIC-14, and by an integrated index of skin changes (lesion area, ultrasound data) will be carried out using two-way analysis of variance with repeated measures, in order to compare scores before and after the treatment.

Safety will be assessed in all patients who received at least one dose of any venoactive drug during the study (studied drugs).

Adverse events will be recorded and analyzed in patients, and all adverse events, serious adverse events, adverse reactions, serious adverse reactions and special situations will be listed.

Ethical considerations:

The study will be conducted in accordance with the principles set out in the Declaration of Helsinki (version adopted in Fortaleza, Brazil, in 2013).

Participants will be fully informed about the program and provide their written consent to participate in it. Treating physician is obliged to indicate in the CRF that the informed consent has been obtained from the patient. The "informed consent" also means that individual discussion with a participant concerning nature of the program and necessity of examinations and evaluations used in the study took place.

The confidentiality of patient data will be guaranteed using identification code numbers (IDs). The relation between the ID and the patient identity will be known only to a treating physician, so that will ensure the anonymity of patient's data.

Data collection:

Treating physician will inform patients about their participation in this program using the Patient Information form (attached to this file). All CRFs filled by a treating physician will be sent to Servier. Data anonymity is guaranteed.

Results:

The obtained data will be used to generate a study report under the supervision of independent scientific experts.

Publication of the results:

Any manuscript containing the results of this study must be submitted to Servier for review before submission to publication. Servier reserves the right to ask for modifications, if necessary.

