2. Description of changes in the quality of life (QoL) measured by the CIVIQ-14 (3):

Variables:

- Global Index Score (GIS) of CIVIQ-14.

3. Description of the adherence to systemic pharmacotherapy as a part of the combination therapy in patients with VUs and CVD of CEAP class C6:

Variables:

- % of patients who continue to use the prescribed VAD at V1, V3 (interim), and V4 visits (if applicable)

^{*} Reference venous ulcer is a primary active venous ulcer, selected by investigator for the follow-up and reporting in the Case Report Form (CRF) in case several ulcers are present in the patient.

The reference VU should meet the following criteria:

- area is no less than 5 cm² but no more than 30 cm²
- phase 2 or 3 of the wound healing process;
- location on the medial aspect of lower third of leg.

- 1) Rutherford RB, Padberg FT Jr, Comerota AJ, Kistner RL, Meissner MH, Moneta GL; American Venous Forum's Ad Hoc Committee on Venous Outcomes Assessment: Venous severity scoring: An adjunct to venous outcome assessment. *J Vasc Surg* 2000;31:1307-1312.
- 4) https://ilyukhin.info/articles/lesionmeter - izmerenie_ploshhadi_jazv. Last accessed: July 7, 2020.

Methods

Each treating physician includes at least 5 patients in the program that meet the inclusion criteria. The inclusion period lasts for 6 months. The treatment will be consistent with routine clinical practice, local label for the medical use of drugs and the specific clinical situation. The following objective methods will be used to assess the changes in the skin condition:

- measurement of the area of reference ulcer (using LesionMeter[†]) before and after the treatment;
- changes in *status localis*.

Duplex ultrasound study (DUS):

- The presence and location of venous reflux and/or occlusion.

Important: Measurement data are recorded for the limb where the reference ulcer is located.

Please note, that DUS will be performed only at the inclusion visit to objectively confirm diagnosis of CVD. Once the diagnosis confirmed, further examination with DUS is not required without specific indications for reevaluation.

Patient management

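### The repeated-measures ANOVA, read as written, is a complete-case V0–V4 comparison: it drops patients without a V4 value and leaves VAS at V1 and V2 unused, although exits may relate to outcome and adherence

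*Combined protocol and SAP*

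**What the plan says.** The Statistical analysis section assigns the group comparison of VAS, VCSS and CIVIQ-14 scores, and of a skin index, to "two-way analysis of variance with repeated measures, in order to compare scores before and after the treatment". The index is described as "by an integrated index of skin changes (lesion area, ultrasound data" and is not defined further. The ANOVA sentence refers only to the groups; the one grouping named in the section is by adherence. The all-included-patients set is stated for baseline characteristics only. No analysis set is named for the effectiveness scores, and no rule for missing values is given.

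The Schedule of the study places VCSS and CIVIQ-14 at V0 and V4, and VAS at every visit. V2 has the footnote "The visit can be replaced by telephone interview which remains at discretion of the doctor-investigator". V3 is conditional: "The visit takes place if the venous ulcer is healed between V2 and V4 visits". The schedule has no early-withdrawal visit.

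The Exclusion criteria, checked at V1 to V4, include "Serious violation or non adherence to the prescribed therapy/ regimen" and an indication for surgery. Methods describes measurement of the reference ulcer area "before and after the treatment".

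**The concern.** A classical repeated-measures ANOVA analyses only patients who have a value at every modelled time point. With two time points, one before and one after treatment, a patient with no V4 score contributes nothing, even if VAS was recorded at V0, V1 and V2.

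That would matter little if V4 values were lost at random. Here two of the stated reasons for leaving are not obviously random. An indication for surgery may reflect how the ulcer is doing. Non-adherence is the characteristic on which the comparison groups are formed, so the rule that defines the groups can also empty one of them. The estimated difference between adherence groups in change from V0 to V4 would then describe only those who stayed, and the plan has no analysis to show how far that differs from the whole cohort. For VAS, the V1 and V2 values record the course of early leavers before they left, and this model ignores them.

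**Working it through.** **Planned size.** Design gives 90 physicians and 450 patients; Methods gives at least 5 patients per physician. 90 × 5 = 450, so the figure reproduces as a recruitment count. It carries no allowance for dropout.

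**Which visits enter the ANOVA.** The stated purpose is a before/after comparison. VCSS and CIVIQ-14 exist only at V0 and V4, and Methods describes area as measured before and after treatment. The consistent reading is V0 and V4. A missing V1 or V2, or an absent V3, then deletes nobody; a missing V4 deletes the patient.

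**Patients retained.** With N = 450 and an assumed fraction m without V4, the number kept is N(1 − m):

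| m (assumed) | Calculation | Kept |
|---|---|---|
| 5% | 450 × 0.95 = 427.5 | about 428 |
| 10% | 450 × 0.90 | 405 |
| 15% | 450 × 0.85 = 382.5 | about 383 |

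**VAS values used.** At full attendance, the four fixed visits give 450 × 4 = 1,800 scheduled values. The before/after model uses 450 × 2 = 900, which is half.

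**Can the loss be selective, and in which direction?** Let h be the true healed share, and d_H and d_U the fractions of healed and unhealed patients without V4. The healed share among those kept is

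h(1 − d_H) / [h(1 − d_H) + (1 − h)(1 − d_U)].

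The Rationale cites 24-week healing of 45% to 83%. The values of d_H and d_U are assumptions.

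| d_H | d_U | Healed share kept, h = 45% | Healed share kept, h = 83% |
|---|---|---|---|
| 10% | 10% | 45.0% | 83.0% |
| 5% | 20% | 49.3% | 85.3% |
| 5% | 30% | 52.6% | 86.9% |
| 20% | 5% | 40.8% | 80.4% |
| 30% | 5% | 37.6% | 78.2% |

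Example, second row with h = 45%: 0.45 × 0.95 = 0.4275; 0.55 × 0.80 = 0.44; 0.4275 / 0.8675 = 0.493.

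Equal loss shifts nothing. Loss of unhealed patients, for example to surgery, makes those kept look better. Loss of healed patients makes them look worse. The documents do not say explicitly whether a patient seen at V3 must still attend V4, so the second pattern is also possible.

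**The case against.** The strongest reply is that the program is descriptive and its before/after ANOVA is a simple summary. VAS, where a better model gains most, is not among the listed primary or secondary variables; it appears only among the effectiveness criteria. The section also plans paired tests and mean differences with confidence intervals over follow-up, and these could use V1 and V2. All of this is fair, and it limits the weight of the point. It does not remove it. The paired tests assess change over time and do not replace the modelled group-by-time comparison. The loss of patients without V4 also affects VCSS, a primary variable.

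A second reply is that a mixed model does not cure exits tied to the adherence grouping. That stands, and it is why a sensitivity analysis is needed.

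Three stronger readings are tempting but unsupported.

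- A reader might infer that because V3 exists only for ulcers healed between V2 and V4, the ANOVA keeps only healed patients. That would follow only if V3 were a level of the model, and the before/after wording excludes it.
- A reader might count patients complete at V1, V2 and V4, which gives much lower numbers. That also describes a model the plan does not propose.
- A reader might infer that those retained are the ones who did well. No dropout rate or pattern is given, and the table of assumed losses shows shifts both ways.

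**Conclusion.** The point holds in a limited form. The group comparison is a complete-case V0–V4 analysis with no stated missing-data method, in a program whose exclusion criteria can remove patients for reasons plausibly linked to outcome and to the adherence groups. The cost in numbers is modest at the assumed rates: 22 to 67 of 450 patients, by subtraction from the counts kept. The cost in validity is a risk whose direction is unknown. With 45% true healing, the assumed loss patterns move the healed share among those kept to anywhere from 37.6% to 52.6%. All missingness rates are assumptions.

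Missing V4 values affect VAS, VCSS and CIVIQ-14 alike; the unused intermediate visits are mainly a VAS matter. The conclusion also assumes that excluded patients have no V4 value. The documents do not state this, but the schedule offers no other route for collecting one.

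**What to change.** - **VAS.** Replace the ANOVA with a linear mixed model for repeated measures on all available V0, V1, V2 and V4 values in all included patients. Use group, visit and group × visit as fixed effects, a within-patient covariance structure and a physician random effect. Report V3 descriptively.
- **Sensitivity.** Add an analysis for data not missing at random, and tabulate exits by reason and adherence group.
- **VCSS and CIVIQ-14.** The same model may be used on V0 and V4. The gain is small, because a patient with only V0 adds little information on change.
- **Ulcer area.** Do not fit a plain linear model to raw area at all visits. V2 may be by telephone, Methods describes area only before and after treatment, and healed ulcers will pile up at zero. Use area only where it was measured and allow for the zeros, for example by analysing healing separately. The combined skin index needs its own definition, since "DUS will be performed only at the inclusion visit to objectively confirm diagnosis of CVD", absent a specific indication to repeat it.
- **Text.** Name the time points and the effectiveness analysis set, and state whether patients seen at V3 still attend V4.

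The cost is revised wording and slightly more analysis work, with no new data. The mixed model relies on missing-at-random, which is an assumption and must be stated as one.
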